ALDS	Ambulatory Lung Diagnosis System
BiaB	Breathlessness diagnostics in a Box
BiaB-algorithm	Breathlessness diagnostics in a Box algorithm, algorithm that forms part of the BiaB-app, contains a decision tree that combines all test results to a clinical interpretation for the BiaB report
BiaB-app	Breathlessness diagnostics in a Box app, software that is part of BiaB which guides the healthcare professional through the steps needed to complete the diagnostic procedures and provides the BiaB report
BiaB-box	Breathlessness diagnostics in a Box box, the yellow box containing all tests and equipment needed to perform the tests and interpretation
BiaB-procedure	Breathlessness diagnostics in a Box procedure, the process of conducting the individual tests in the BiaBbox, using the BiaB-app and receiving the BiaB-report by healthcare professionals
BiaB-report	Breathlessness diagnostics in a Box report, the report that is generated based on the tests performed as part of the BiaB procedure
BNP	B-type Natriuretic Peptide
COPD	Chronic Obstructive Pulmonary Disease
CONSORT	Consolidated Standards of Reporting Trials

СТРА	Computed Tomography (CT) Pulmonary Angiogram, a medical diagnostic test to obtain an image of the pulmonary arteries				
CVD	Cardiovascular Disease				
ECG	Electrocardiogram				
eCRG	Electronic Case Report Form				
EDC	Electronic Data Capture				
ENCePP	European Network of Centres for Pharmacoepidemiology and Pharmacovigilance				
EQ-5D-5L	EuroQol 5-Dimension 5-Level, standard layout for recording an adult person's current self-reported health state, consists of a standard format for respondents to record their health state according to the EQ-5D-5L descriptive system and the EQ VAS				
ERS	European Respiratory Society				
GDPR	General Data Protection Regulation				
GP	General Practitioner				
GPRI	General Practitioners Research Institute				
ICF	Informed Consent Form				
IRB	Institutional Review Board				
HF	Heart Failure				
НСР	Healthcare Professional				
NT-proBNP	N-terminal pro-B-type Natriuretic Peptide				
PE	Pumonary Embolism				

PHQ-4	Patient Health Questionnaire
SAB	Scientific Advisory Board
SAE	Serious Adverse Event
SpO2	Peripheral oxygen saturation
SWGRT	Stepped-Wedge Group-Randomized Trial
VTE	Venous thromboembolism
WMO	Medical Research Involving Subjects Act
WPAI	Work Productivity and Activity Impairment questionnaire

SUMMARY

Rationale: Breathlessness has a prevalence of ~10% and is a common reason for people to consult their general practitioner. As breathlessness is a symptom in various conditions it is difficult to determine its cause, which hampers optimal treatment. There is a lack of quick and easy tests that can be used in primary care to diagnose the cause of breathlessness. Therefore, we have developed "Breathlessness diagnostics in a Box (BiaB)", an easy and reliable tool intended to support healthcare professionals with fast execution of diagnostic procedures required to diagnose the cause(s) of breathlessness. In 2023 a pilot study was performed to design and test BiaB. In the current study, we aim to investigate whether implementation of BiaB in primary care will shorten the time for the diagnostic process for patients presenting with breathlessness.

Objectives:

Objectives	Endpoints				
Primary					
1. To demonstrate whether BiaB use	Days between presentation with or				
shortens time to diagnosis as compared to	consultation for breathlessness and a				
usual care without BiaB use.	diagnosis causing the breathlessness (usual				
	care group versus BiaB intervention group)				
Secondary					
2. To demonstrate whether BiaB use	Number of newly diagnosed patients with				
increases the number of new diagnoses of	COPD and heart disease (usual care group				
COPD and heart disease as compared to	versus BiaB intervention group)				
usual care without BiaB use.					
3. To demonstrate usability and efficiency	Frequency of use of:				
of BiaB.	• BiaB				
	 Lung function tests 				
	 ECG measurements 				
	Frequency of:				
	 Referral to specialist (and type) 				
	 Acute hospital admission 				
	 Emergency room visits 				

Clinical outcomes
Economic analysis
Qualitative evaluation of the implementation of BiaB

Study design: In this study the implementation of BiaB in primary care will be evaluated. A total of 45 practices (900 patients) will be included in the Netherlands, Spain, and Portugal, with the option to expand to other countries. A stepped-wedge study design will be used with a randomised timing of BiaB implementation in general practices. The design includes a control period of 6-30 weeks, a transition period of 4 weeks, and a BiaB period of 3-30 weeks. Each practice will actively participate in the study for 40 weeks.

Study population:

- 1. Patients with undiagnosed dyspnea (breathlessness)
- 2. Patients who have existing diseases that could cause breathlessness but have residual or increasing breathlessness that could be caused by other not yet detected diseases. Or HCP has doubts or requires additional tests to confirm diagnosis or to suspect new, parallel, diagnoses. For example, breathlessness in patients assessed:
 - a. within the framework of Cardiovascular Risk Management
 - b. for COPD monitoring

Patients with acute worsening of previous diagnosed chronic disease where there is no suspicion of comorbidities (for example when a patient with clear COPD diagnosis has an exacerbation where typically the HCP will not perform additional tests) will be excluded from the study.

Intervention: All general practices will start with a control period, during which healthcare professionals will obtain consent from eligible participants to collect data and perform consultations as usual. At a certain timepoint, defined by randomisation, they will be assigned to use BiaB. From this moment on, visiting patients that meet inclusion criteria will be asked to partake in the study. After consent, healthcare professionals will use BiaB during patient

consultations/diagnostic workup. The BiaB-box contains questionnaires (YEARS, PHQ-4), point of care tests (NT-proBNP, D-dimer, pulse oximeter), an oscillometer and an ECG device. The BiaB-App will guide the healthcare professional (clinician, nurse, practice assistant) through the steps of diagnostic procedures within the BiaB-box. The BiaB-algorithm, developed by the GPRI team in collaboration with the international scientific advisory board, uses input from these tests to support the healthcare professional with interpretation of test results and generates the BiaB-report.

Ethical considerations and extent of the burden: Study specific involvement for patients presenting with breathlessness is limited to one visit for the patient and four follow-up questionnaires. The patients will receive medical care as determined by their physician. The BiaBbox contains non- and minimally invasive tests, limited to questionnaires, oscillometry which requires tidal breathing, an ECG and a finger stick point of care test. This test might cause a slight inconvenience for the patient but the risks of participating in the study are deemed to be negligible. Follow-up data will be collected by healthcare professional reported outcomes and patient reported outcomes in the form of short questionnaires up to one year for the patients.

1. INTRODUCTION

Breathlessness is a common reason for people to consult their healthcare professional (HCP) and can have various causes, including psychological factors. However, in most cases, the origin is pulmonary or cardiovascular. HCPs (e.g., general practitioner, practice assistant, practice nurse, clinician) often find it challenging to distinguish between different causes of breathlessness because distinguishing dyspnea causes in primary care is hard with limited diagnostics. Referral to secondary care may be needed if the cause is unclear or initial treatment fails. A Danish study conducted in a hospital dyspnea clinic found that the initial diagnosis made by the HCP was correct in only 31% of patients referred to cardiologists and in 58% of patients referred to pulmonologists. This discrepancy may lead to delays in correct diagnosis and proper treatment. Moreover, there is considerable overlap between both causes of breathlessness, which requires an integrated approach. The Danish study revealed that heart failure was the sole cause in 17% of cases, pulmonary disease in 35%, and combined heart and lung disease in 14% of 284 patients examined.

In a large study of a middle-aged Swedish population, the primary conditions contributing to breathlessness included respiratory disease, anxiety or depression, obesity, and heart disease or chest pain, with a high level of overlap (Figure 1). ³ Notably, 66% of the examined participants (n=1097) had two or more of these conditions.

[figure not shown]

Figure 1. Overlap of underlying contributing conditions to breathlessness

Investigations into patients presenting with breathlessness in general practice often lack a structured approach and clear guidance. A study using a large UK electronic medical database, which analysed adults presenting with breathlessness, revealed that haemoglobin testing was

conducted in 69% of patients, though anaemia was diagnosed in only 5% of cases. Moreover, after two years, most patients (57%) still had no relevant diagnosis recorded.⁴

A Dutch study assessing the efficiency of integrated care provided by both a cardiologist and a pulmonologist found that patients received diagnoses nearly one month earlier than through consultations with non-integrated specialists. ¹

A recent literature review on incorporating clinical tools into a clinical decision support system for primary care, aimed at efficiently and accurately diagnosing chronic dyspnea, suggested a staged approach to testing. Initially, after history taking and physical examination, simple tests such as spirometry, pulse oximetry (SpO₂), and electrocardiography (ECG) should be performed.⁵ If the diagnosis remains uncertain, the next step involves additional tests, including chest X-ray, full blood count, thyroid function tests, and N-terminal pro-B-type Natriuretic Peptide (NT-proBNP test). Patients who remain undiagnosed are then referred for advanced testing, such as thoracic CT scans or echocardiograms (Figure 2).3⁵

[figure not shown]

Figure 2. A summary of the stepwise approach for dyspnea assessment and the probability of elucidating the causal diagnosis based on included studies of the literature review of Sunjaya et al.⁵

Although the tests from the stepwise approach by Sunjaya et al. are available in many settings, the process of ordering, performing, and acquiring results often requires multiple appointments at different locations, leading to diagnostic delays. There is currently a lack of quick and easy tests for HCPs to diagnose the cause of breathlessness. Therefore, we have developed "Breathlessness diagnostics in a Box (BiaB)", an easy and reliable tool intended to support HCPs with fast execution of diagnostic procedures required to identify the underlying cause of breathlessness (Figure 3).

[figure not shown]

Figure 31. Content of the BiaB box

The BiaB-box includes the following devices: an iPad, an Oscillometer (the Ambulatory Lung Diagnosis System (ALDS)), an ECG, a point-of-care device to test D-dimer and NT-proBNP tests, and an SpO₂ meter. The BiaB-application (BiaB-app) guides the HCP through the necessary steps for conducting tests and collecting essential data, such as clinical history, questionnaires. The BiaB-app is also a platform of other applications (ALDS, ECG, ECG overread, Castor eCRF, point-of-Care), facilitating the interpretation and integration of the results of the tests that are included in BiaB. Upon completion of the BiaB steps, the application provides a report for the HCP as a guidance for the diagnosis in patients with breathlessness, based on the BiaB decision tree (section 5.1.7).

In 2023 a pilot study was performed to design and test BiaB. In this pilot study, 5 general practices and 122 patients were included. HCPs and patients co-designed the tool (unpublished data). The decision-tree within the BiaB-app successfully provided diagnostic reports based on input from the ECG, oscillometer and NT-proBNP tests to support HCPs. During the pilot study the BiaB-app and individual tests were positively perceived by HCPs and patients.

In the current study, we aim to investigate implementation of BiaB in more general practices in the Netherlands, Spain, and Portugal and potentially other countries (a total of 45 practices, 900 patients) to determine whether implementation of BiaB in primary care will reduce the time between presentation of breathlessness at the HCP and the diagnosis of a cause leading to the breathlessness.

2. OBJECTIVES

Primary objective:

• To demonstrate whether BiaB use shortens time to diagnosis as compared to usual care without BiaB use.

Secondary objectives:

- To demonstrate whether BiaB use increases the number of new diagnoses of COPD and/or heart disease as compared to usual care without BiaB use
- To demonstrate usability and efficiency of BiaB.

3. Study design

A prospective stepped-wedge study design will be used for this study (Figure 4). In every country, participating sites will be assigned randomly to one of the five sequences (3 sites per sequence) for timing of the intervention start. Each sequence starts with a usual care period (6 weeks or a multiple of 6) which will be followed by a transition period of 4 weeks prior to the BiaB intervention

period (6 weeks or a multiple of 6). During the transition period the healthcare professionals (HCPs) at the site will be instructed about the start date of the BiaB intervention and they will receive training for the use of BiaB. The study duration for sites is 40 weeks in total. The maximum study duration for patients is one visit followed by a maximum of 4 quarterly questionnaires (1 year).

There will be 15 sites per country, amounting to a total of 45 sites for The Netherlands, Spain and Portugal. Per site 20 patients will be included for analysis during the 40-week study period, amounting to 300 patients per country and 900 in total for 3 countries. Per site the number of patients seen in the usual care period and BiaB intervention period will differ, but at the end of the study this study design should yield a ratio of 1:1 (usual care or BiaB intervention).

[figure not shown]

Figure 42. BiaB stepped-wedge study design. All sites (15 per participating country) will be randomly assigned to one of the sequences with set periods of usual care, transition, and BiaB intervention. In total 20 patients will be included per site, amounting to 300 patients per country and 900 patients in total.

Data will be collected (i) during the visit, and (ii) using questionnaires sent to patients and HCPs. Electronic medical data will be extracted from the participating GP practices before, during and at the end of the study. Data collected during the usual care period and, if possible, retrospective data will be used as a control to examine endpoints.

4. Study population

This study aims to capture the real-world heterogeneity in primary care practices and patients. Therefore, inclusion and exclusion criteria are limited.

4.1 Inclusion criteria

Patients are eligible to be included in the study if the following criteria apply:

Age

1 Patient must be at least 18 years old at the time of signing the informed consent.

Type of patients and symptom characteristics

- 2a Patients that present with undiagnosed dyspnea (breathlessness); or
- Patients who have existing diseases that could cause breathlessness, but have residual or increasing breathlessness that could be caused by other not yet detected diseases. Or HCP has doubts or requires additional tests to confirm diagnosis or to suspect new, parallel, diagnoses. For example, breathlessness in patients assessed:
 - a. within the framework of Cardiovascular Risk Management or
 - b. for COPD monitoring

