4.2 Exclusion criteria

- Acute worsening of previous diagnosed chronic disease where there is no suspicion of comorbidities (for example when a patient with clear COPD diagnosis has an exacerbation where typically the HCP will not perform additional tests).
- 2. Inability to understand and sign the written consent form.

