6.1.3 Other study parameters

During the consultations the HCP will collect medical history and perform physical examination (or take from the medical record if the BiaB visit is not performed by the general practitioner)

The following parameters will be collected:

- Reason for the BiaB box:
 - o New breathlessness, with no previous diagnosis
 - Breathlessness in existing diseases that could cause breathlessness, but have residual or increasing breathlessness that could be caused by other not yet detected diseases
- Differential diagnosis prior to BiaB tests (yes, no, type)
 - Suspected heart failure
 - Suspected ischemic heart disease
 - Suspected asthma
 - Suspected COPD
 - Suspected anxiety/depression
- Patient information (age, sex, height, weight, smoking status)
- Reason for visit
- Medical history (COPD, Asthma, allergy/hyperreactivity, eosinophilia, cardiac disease, anxiety, depression, chest operations, rhinosinusitis)

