6.3 Study procedures

Data collection will take place during the BiaB visit, retrospectively, and after the visit during the follow-up period. See the Schedule of Assessments with an overview of all performed procedures (Table 1).

Table 1. Schedule of assessments for usual care and BiaB intervention period.

Schedule of assessments (usual care period)								
Visit	Visit 01	Visit 11	Follow up 1	Follow up 2	Follow up 3	Follow up 4		
Time (months)	0	0	3 (+14 days)	6 (+14 days)	9 (+14days)	12 (+14 days)		
Invitation + Informed consent	Invitation + Informed consent							
Invitation and informed consent provided	Χ							
Informed consent procedure		Х						
Patient reported outcomes (electronic) ²								
WPAI		Х	X	Х	Χ	Х		
EQ-5D-5L		Х	Х	Х	Χ	Х		
Healthcare utilization		Х	X	Х	Х	Х		
NRS dyspnea		Х	Х	Х	Х	Х		
Diagnosis questionnaire		Х	Χ	Χ	Χ	Х		

Schedule of assessments (BiaB intervention period)							
Visit	Visit 01	Visit 1 ¹	Follow up 1	Follow up 2	Follow up 3	Follow up 4	
Time (months)	0	0	3 (+14 days)	6 (+14 days)	9 (+14days)	12 (+14 days)	
Invitation + Informed consent							
Invitation and informed consent provided	Χ						
Informed consent procedure		Х					
BiaB visit							
Patient characteristics		Х					
YEARS questionnaire + D-dimer test (optional)		Х					
SpO2 measurement		Χ					
NT-proBNP test		Х					
PHQ-4 questionnaire		Х					
ECG		Х					
Oscillometry		Χ					
Patient reported outcomes (electronic) ²							
WPAI		Х	Χ	Χ	Χ	Х	
EQ-5D-5L		Х	Х	Х	Χ	Х	
Healthcare utilization		Х	Х	Х	Х	Х	
NRS dyspnea		Х	Χ	Х	Х	Χ	
Diagnosis questionnaire		Х	Χ	Х	Х	Χ	

1 VO and V1 can be at the same moment if regulations allow
2 (electronic) patient reported outcome ((e)PRO), see section 6.3.2

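### HCPs enrol patients knowing their study period, one entry limb depends on their inclination to test, and the items that would show a resulting case-mix shift are worded for BiaB only

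*Protocol*

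**What the plan says.** **Entry.** Protocol section 4.1 gives two clinical routes. Route 2a is "Patients that present with undiagnosed dyspnea (breathlessness); or". The second route covers existing disease with residual or increasing breathlessness that another, undetected disease might explain. It then adds a further limb: "Or HCP has doubts or requires additional tests to confirm diagnosis or to suspect new, parallel, diagnoses". The Summary repeats this limb.

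**Who enrols, and when.** The Summary (Intervention) says: "All general practices will start with a control period, during which healthcare professionals will obtain consent from eligible participants". After the site is assigned to BiaB: "From this moment on, visiting patients that meet inclusion criteria will be asked to partake in the study". Under section 3, HCPs are, during the transition period, "instructed about the start date of the BiaB intervention and they will receive training for the use of BiaB". Section 6.2 has the allocation list generated by an uninvolved researcher once all sites in a country are recruited.

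**What is recorded at entry.** Section 6.1.3 lists an item for the reason the box is used, with two options (new breathlessness, or breathlessness in existing disease). It also lists "Differential diagnosis prior to BiaB tests (yes, no, type". Age, sex, smoking status, reason for visit and medical history follow without mention of BiaB. In Table 1 the part titled "Schedule of assessments (usual care period") holds only consent and patient-reported outcomes; a patient-characteristics row appears only in the BiaB part, under the BiaB visit. Section 6.3.3 has HCPs report patient characteristics and medical information at Visit 1, with no limit to one period.

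**What is to be reported.** Section 8.1.2 says that analyses will be presented for the different study populations.

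**The concern.** In a stepped-wedge trial where each patient is enrolled once, the usual-care and BiaB groups are different people. Randomising the switch date balances sites over calendar time. It does not balance the patients whom an HCP chooses to enrol before and after the switch. If the box makes an HCP readier to investigate, a patient under COPD monitoring might not be thought to need further tests in usual care, yet be enrolled once the tests are at hand.

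Such a change would coincide with the switch in each site. Neither a period effect nor a clustering adjustment would remove it, and a larger sample would only estimate the biased contrast more precisely. Both the primary endpoint (days to diagnosis) and the first secondary endpoint (new COPD and heart disease diagnoses) depend on how many enrolled patients already have a known disease.

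The protection available is to record why each patient entered and what was suspected beforehand, in the same way in both periods. If the control-period sites do not collect this, no later analysis plan can supply it.

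**Working it through.** **1. Which entry conditions depend on the HCP's inclination to test?**

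| Condition (Protocol) | What it turns on | Depends on inclination to test? |
|---|---|---|
| 4.1, route 2a | Undiagnosed breathlessness | No |
| 4.1, second route, first limb | Existing disease, residual or increasing breathlessness | Not directly |
| 4.1, second route, further limb | HCP doubt or need for tests | Yes |
| 4.2, exclusion 1 | No suspicion of comorbidities | Only through its example |

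**2. Is the period known at enrolment?** Yes. HCPs know the start date, are trained, and have the box. No blinded eligibility check and no identification of patients before the period is known is described. The independent list in section 6.2 protects the choice of sites, not of patients.

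**3. Could a shift be seen with the data as specified?**

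| Variable | Wording in 6.1.3 | Collected in usual care? |
|---|---|---|
| Entry route | Reason for using the box, two options | Not if read literally |
| Pre-test differential | Prior to BiaB tests | Not if read literally |
| Age, sex, smoking, history | Neutral | Yes, by 6.1.3 and 6.3.3; no row in the usual-care part of Table 1 |

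The entry item has no option for the HCP-doubt limb, so even in the BiaB period that limb cannot be separated from the rest. Read literally, the by-population presentation in section 8.1.2 would have no entry-route item to classify control patients.

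**4. Size, as illustration only.** The plan's target (section 4.3) is 20% of 70 days: 0.20 × 70 = 14 days. The documents give neither the share of patients by route nor their times to diagnosis, so what follows uses assumed values and a BiaB effect of zero.

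Spurious difference = (change in share of a route) × (difference in mean days between routes).

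- Assumed gap 30 days; shift 10, 20, 30 points: 30 × 0.10 = 3; 30 × 0.20 = 6; 30 × 0.30 = 9 days. Divided by 14: 21%, 43%, 64%.
- Other assumptions: usual-care mean 70 days and a discretionary share of 20% in usual care, rising to 30–50% with BiaB. The mean in the remaining patients is (70 − 0.2 × mean of the discretionary group) / 0.8.
  - Discretionary mean 50 days, share 30%: rest (70 − 10)/0.8 = 75; 0.1 × (50 − 75) = −2.5 days.
  - Discretionary mean 20 days, share 50%: rest (70 − 4)/0.8 = 82.5; 0.3 × (20 − 82.5) = −18.8 days.
  - Discretionary mean 100 days, share 30%: rest (70 − 20)/0.8 = 62.5; 0.1 × (100 − 62.5) = +3.8 days.
  - Discretionary mean 140 days, share 50%: rest (70 − 28)/0.8 = 52.5; 0.3 × (140 − 52.5) = +26.2 days.

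The sign follows the assumption made about which patients are diagnosed faster. The documents do not settle that.

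**The case against.** Several counter-arguments have force.

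- **A reader might infer that eligibility as a whole rests on HCP doubt.** It does not. Route 2a and the first limb of the second route do not turn on it.
- **A reader might infer that the exclusion turns on whether the HCP would test.** The words "where typically the HCP will not perform additional tests" stand inside an example. The operative condition is the absence of suspected comorbidity. That is still a judgement, but not one about testing.
- **A reader might infer that baseline data are collected in the BiaB period only.** Most of section 6.1.3 is neutral, and section 6.3.3 applies to Visit 1 in both periods. HCP-reported items have no rows in either part of Table 1, and the BiaB characteristics row may simply reflect input to the algorithm. What stands is the wording of two items and a schedule that does not match section 6.3.3.
- **The mechanism is conjecture.** Needing tests can mean clinical need, and sections 5.1.2, 5.1.3 and 5.1.6 call ECG, NT-proBNP and oximetry common in primary care. This is fair: the risk is plausible, not shown.
- **Results by study population would expose a shift in route mix.** They would, if entry route is recorded in usual care. They would not show selection within a route or correct the overall comparison.
- **Covariate adjustment belongs in the analysis plan.** Agreed; its absence from the protocol is no defect. Data capture, however, has to be settled in the protocol.
- **Limited criteria serve the real-world aim of section 4.** That is a sound reason not to insist on rewriting the criteria.

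**Conclusion.** The concern holds in a limited form. HCPs enrol with knowledge of the period, one limb of one entry route depends on their readiness to investigate, and randomising the switch date does not prevent case mix from differing between periods. Neither direction nor amount can be stated from the documents. The 3 to 9 days and the wider range of about −19 to +26 days rest wholly on assumed gaps and shifts, and show only that a shift could matter against a 14-day target.

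The firm defect is one of recording. Entry route and pre-test differential are worded for BiaB only, the entry item omits the HCP-doubt limb, and the usual-care part of Table 1 lacks a row that section 6.3.3 implies. The change should be made before enrolment, because what was suspected before testing may not be recoverable afterwards. The documents do not show that enrolment will be biased or that the comparison is invalid.

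**What to change.** 1. In section 6.1.3, rename the first item to *Reason for study entry*, with three options: route 2a; existing disease with residual or increasing breathlessness; HCP doubt or need for tests. Word the differential diagnosis as prior to any test.
2. Record both at Visit 1, before any test, on the same form in both periods. Add a patient-characteristics row to the usual-care part of Table 1 so that it agrees with section 6.3.3.
3. Compare enrolment and baseline mix by period. The number of patients presenting with breathlessness, already listed in section 6.1.2.1, can serve as the denominator if it is counted by period.
4. In the analysis plan, adjust the primary and first secondary comparisons for entry route, age, sex, smoking status and prior COPD, asthma or cardiac disease. Add a sensitivity analysis limited to route 2a. Neither removes selection within a route on unrecorded features, since the same HCP also chooses the 2a patients.

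The cost is wording in section 6.1.3 and Table 1, and slightly more data entry in the control period. The eligibility criteria can stay as they are.
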